### 8.5.3 Analysis of Secondary Endpoints

#### Efficacy Endpoints

Summary statistics as described in Section [8.5.1](#) will be used for the summary of efficacy endpoints by dose level. The 95% exact Clopper Pearson confidence intervals (CIs) will be used for binary endpoints.

Posterior probabilities assuming a beta (1,1) prior for the binary efficacy endpoints will also be estimated.

Kaplan-Meier estimates (product-limit estimates) will be presented for the analysis of PFS together with a summary of associated statistics (median survival time, 6-, 12-month survival rate estimates and estimates for every 6 months thereafter if applicable) including the corresponding 2-sided 95% CIs. The CIs for the median will be calculated according to Brookmeyer and Crowley (7) and CIs for the survival function estimates at above defined time points will be derived using the log-log transformation according to Kalbfleisch and Prentice (20). The estimate of the standard error will be computed using Greenwood's formula.

The Safety Analysis Set will be used for the efficacy analyses in Part I of the study.

CCI

[REDACTED]

[REDACTED]

CCI

CCI

[REDACTED]

[REDACTED]

#### 8.5.4 Pharmacokinetic Calculations

M4112 plasma concentrations will be listed, summarized, and graphically displayed by treatment and time point. Derived PK parameters will be listed and summarized by treatment. Descriptive summaries of plasma concentrations and derived PK parameters of M4112 will be presented for the PK analysis set. The PK variables will be summarized by the number of observations, mean, geometric mean, median, SD, standard error of mean, minimum, maximum, and/or coefficient of variation. Concentration values below the lower limit of quantification will be taken as zero for descriptive statistics.

Individual plasma and mean ( $\pm$ SD) concentration time plots will be provided for each treatment using a linear and semi-logarithmic scale.

Graphical displays will be given, where appropriate. Details of the statistical analysis, including evaluation of dose proportionality and comparison of parameters between single agent treatment CCI will be described further in the iAP.

A PopPK model will be constructed to allow for calculation of population pharmacokinetic parameters for M4112 and the analysis of selected covariates. PopPK analyses will be detailed in a separate analysis plan.

#### 8.5.5 Concentration-QTc analysis

Time-matched, replicate ECGs and PK samples collected in the dose-escalation phase will be used to analyze for cQTc responses using slope analysis of exposure/response. Analyses will be further detailed in a separate analysis plan.

#### 8.5.6 Analysis of Safety and Other Endpoints

Safety analyses will be performed on the Safety Analysis Set. The safety endpoints will be tabulated by dose-level, using descriptive statistics. Further details will be provided in the iAP based on current safety experience applying the latest MedDRA version.

## Adverse Events

All AEs will be coded according to MedDRA. Severity of AEs will be graded using the NCI-CTCAE 4.03 toxicity grading scale.

AEs will be summarized according to MedDRA System Organ Classes (SOCs) and Preferred Terms. The incidence of the following will be analyzed:

- TEAEs and SAEs
- TEAEs and SAEs related to study treatment
- TEAEs with CTCAE Grade  $\geq 3$
- TEAEs with CTCAE Grade  $\geq 3$  related to study treatment
- TEAEs leading to withdrawal, dose modifications, temporary and permanent interruptions of study drug, and death.

AESIs will be summarized according to MedDRA SOCs and Preferred Terms.

Of note, missing classifications concerning relationships with study treatment will be considered related to the study treatment.

Subjects who terminated treatment will be summarized by primary withdrawal reason by dose level.

All deaths after first dose of study treatment as well as reasons for death will be tabulated.

## Laboratory Values

Laboratory results will be classified by grade according to NCI-CTCAE 4.03. The worst on-treatment grades for chemistry and hematology laboratory results will be summarized. Shifts in toxicity grading from baseline to highest grade during the on-treatment period will be displayed. For laboratory tests without an NCI-CTCAE grade definition, results will be presented categorically (eg, below, within, or above normal limits).

## Physical Examination Results and Electrocardiograms

Physical examination, including vital signs (body temperature, respiratory rate, heart rate, and blood pressure) and ECG, recorded at baseline and after drug administration will be presented. The ECG parameters will be summarized by descriptive statistics per time point, and changes from baseline will be calculated. Data will be further analyzed using concentration effect modeling for baseline corrected QTcF values. Time-matched replicate ECGs will be analyzed along with M4112 plasma concentrations in a cQTc analysis as described in Section 8.5.3.

CCI

## 8.6

### Interim and Additional Planned Analyses

This is an exploratory study. Available data will be evaluated during the study by the SMC.

The SMC will review the data during the conduct of the study. The cut off for dose escalation assessments by the SMC will usually be triggered by the completion of Cycle 1 (or dropout) of the last subject in the respective dose escalation cohort of usually 3 subjects. In cases where enrollment of last subject in a dosing cohort is delayed, the SMC may decide (based on available data) upon enrollment and dose for the next dosing cohort before all subjects in a cohort have completed Cycle 1. The Bayesian model will then be updated with the available data, and the data from the subject not having completed Cycle 1 at time of SMC will be considered in the next SMC.

The cut off for an exploratory interim analysis of the safety and preliminary antitumor activity data from the complete single agent dose escalation will be triggered when the last subject enrolled in monotherapy dose escalation reaches the first on-treatment tumor assessment or experiences death or premature withdrawal for any reason, whichever comes first.

CCI

The main analysis of the study is planned to occur after the objectives of the study can be answered.

## 9

### Ethical and Regulatory Aspects

#### 9.1

#### Responsibilities of the Investigator

The Investigator is responsible for the conduct of the study at the site and will ensure that the study is performed in accordance with this protocol, the ethical principles outlined in the Declaration of Helsinki, ICH GCP, and any other applicable regulations. The Investigator must ensure that only subjects who have given informed consent are included in the study.

According to United States Code of Federal Regulations Part 54.2 (e), for studies conducted in any country that could result in a product submission to the US FDA for marketing approval and could contribute significantly to the demonstration of efficacy and safety of an IMP (which are considered “covered clinical studies” by the FDA), the Investigator and all subinvestigators are obliged to disclose any financial interest which they, their spouses or their dependent children may have in the Sponsor or the Sponsor’s product under study. This information is required during the study and for 12 months following completion of the study.

#### 9.2

#### Subject Information and Informed Consent

An unconditional prerequisite for a subject’s participation in the study is his/her written informed consent. The subject’s written informed consent to participate in the study must be given before any study-related activities are carried out. CCI

CCI

[REDACTED]. Adequate information must therefore be given to the subject by the Investigator or appropriate designee (if local regulations permit) before informed consent is obtained.

A subject information sheet must be prepared in the local language in accordance with ICH GCP and will be provided by the Sponsor for the purpose of obtaining informed consent. In addition to providing this written information to a potential subject, the Investigator or a designate will inform the subject verbally of all pertinent aspects of the study, using language chosen so that the information can be fully and readily understood by laypersons. The subject will be given sufficient time to read the information and the opportunity to ask questions and to request additional information and clarification.

If permitted by national regulations, a person other than the Investigator may inform the subject about the study and sign the ICF, as above.

After the information is provided by the Investigator, the ICF must be signed and dated by the subject and the Investigator.

The signed and dated declaration of informed consent will remain at the Investigator's site, and must be safely archived by the Investigator so that the forms can be retrieved at any time for monitoring, auditing, and inspection purposes. A copy of the signed and dated information and ICF should be provided to the subject prior to participation.

Whenever important new information becomes available that may be relevant to the subject's consent, the written subject information sheet and any other written information provided to subjects will be revised by the Sponsor or designee and be submitted again to the IEC/IRB for review and favorable opinion. The agreed, revised information will be provided to each subject in the study for signing and dating. The Investigator will explain the changes to the previous version. The subject will be given sufficient time to read the information and the opportunity to ask questions and to request additional information and clarification about the changes.

### 9.3 Subject Identification and Privacy

A unique number will be assigned to each subject, immediately after informed consent has been obtained. This number will serve as the subject's identifier in the study as well as in the clinical study database. All subject data collected in the study will be stored under the appropriate subject number. Only the Investigator will be able to link study data to an individual subject via an identification list kept at the site. For each subject, original medical data will be accessible for the purposes of source data verification by the Medical Monitor, audits and regulatory inspections, but subject confidentiality will be strictly maintained.

Data protection and privacy regulations will be observed in capturing, forwarding, processing, and storing subject data. Subjects will be informed accordingly, and will be requested to give their consent on data handling procedures in accordance with national regulations.

## CCI

During this time, the samples may be reanalyzed for newly identified markers or with new or improved technology. After 10 years, the samples will be destroyed or fully anonymized or a new IEC/IRB approval and informed consent will be requested to keep the samples for an additional period. If tumor tissue remains, the site will be notified and the tumor tissue will be returned to the site upon request. If the site does not request the return of the tumor tissue, it will be destroyed.

## 9.4 Emergency Medical Support and Subject Card

Subjects will be provided with Emergency Medical Support cards supplied by the study site for use during study participation in order to provide clinical study subjects with a way of identifying themselves as participating in a clinical study and to give health care providers access to any information about this participation that may be needed to determine the course of medical treatment for the subject.

The first point of contact for all emergencies will be the clinical study Investigator caring for the affected subject. The Investigator agrees to provide his or her emergency contact information on the card for this purpose. If the Investigator is available when an event occurs, they will answer any questions. Any subsequent action will follow the standard process established for Investigators.

In cases where the Investigator is not available, the Sponsor or designated CRO will provide the appropriate means to contact a Sponsor/CRO physician. This includes the provision of a 24 h contact number at a call center, whereby the health care providers will be given access to the appropriate Sponsor/CRO physician to assist with the medical emergency.

## 9.5 Clinical Study Insurance and Compensation to Subjects

Insurance coverage will be provided for each country participating to the study. Insurance conditions shall meet good local standards, as applicable.

## 9.6 Independent Ethics Committee or Institutional Review Board

Prior to commencement of the study at a given site, this clinical study protocol will be submitted together with its associated documents (eg, ICF) to the responsible IEC or IRB for its favorable opinion or approval, which will be filed in the Investigator Site File. A copy will be filed in the Sponsor Trial Master File at the CRO.

The IEC or IRB will be asked to document the date of the meeting at which the favorable opinion or approval was given and the members and voting members present. Written evidence of favorable opinion or approval that clearly identifies the study, the clinical study protocol version and the Subject Information and ICF version reviewed should be provided. Where possible, copies of the meeting minutes should be obtained.

Amendments to this clinical study protocol will also be submitted to the concerned IEC or IRB, before implementation of substantial changes (see Section 10.5). Relevant safety information will be submitted to the IEC or IRB during the course of the study in accordance with national regulations and requirements.

## **9.7                   Health Authorities**

The clinical study protocol and any applicable documentation (for example, Investigational Medicinal Product Dossier, Subject Information, and ICF) will be submitted or notified to the Health Authorities in accordance with all local and national regulations for each site.

# **10                   Study Management**

## **10.1               Case Report Form Handling**

Refer to the Manual of Operations for eCRF handling guidelines.

The main purpose of the eCRF is to obtain data required by the clinical study protocol in a complete, accurate, legible and timely. The data in the eCRF should be consistent with the relevant source documents.

The Investigator or designee is responsible for ensuring that the data collected in the course of this study is accurate and documented appropriately on all applicable forms. They will then be processed, evaluated, and stored in anonymous form in accordance with applicable data protection regulations. The Investigator must ensure that the eCRFs and any other associated documents forwarded to Sponsor or its designated organization contain no mention of any subject names.

The data will be entered into a validated database. The Sponsor or its designee will be responsible for data processing, in accordance with the Sponsor's data management procedures. Database lock will occur once quality control and quality assurance procedures have been completed. PDF files of the eCRFs will be provided to the Investigators at the completion of the study.

## **10.2               Source Data and Subject Files**

The Investigator must keep a file (medical file, original medical records) on paper or electronically for every subject in the study. It must be possible to identify each subject by using this subject file. This file will contain the demographic and medical information for the subject listed below and should be as complete as possible.

- Subject's full name, date of birth, sex, height, weight
- Medical history and concomitant diseases
- Prior and concomitant therapies (including changes during the study)
- Study identification, that is, the Sponsor study number for this clinical study, and subject number

- Dates for entry into the study (informed consent) and visits to the site
- Any medical examinations and clinical findings predefined in this clinical study protocol
- All AEs
- Date that the subject left the study including any reason for early withdrawal from the study or IMP (if applicable).

All documents containing source data must be filed, including, but not limited to CT or MRI scan images, ECG recordings, and laboratory results. Such documents must bear the subject number and the date of the procedure. If possible, this information should be printed by the instrument used to perform the assessment or measurement. As necessary, medical evaluation of such records should be performed; all evaluations should be documented, signed, and dated by the Investigator.

Electronic subject files will be printed whenever the Monitor performs source data verification. Printouts must be signed and dated by the Investigator, countersigned by the Monitor and kept in a safe place at the site.

### **10.3                   Investigator Site File and Archiving**

Upon initiation of the study, the Investigator will be provided with an Investigator Site File containing all necessary study documents, which will be completed throughout the study and updated as necessary. The file must be available for review by the Monitor, during Sponsor audits and for inspection by Health Authorities during and after the study, and must be safely archived for at least 15 years (or longer, per local requirements or as otherwise notified by the Sponsor) after the end of the study. The documents to be archived include the Subject Identification List and the signed subject ICFs. If archiving of the Investigator Site File is no longer possible at the site, the Investigator must notify the Sponsor/designee.

All original subject files (medical records) must be stored at the site (hospital, research institute, or practice) for the longest possible time permitted by the applicable regulations, and/or as per ICH GCP guidelines, whichever is longer. In any case, the Investigator should ensure that no destruction of medical records is performed without the written approval of the Sponsor.

### **10.4                   Monitoring, Quality Assurance, and Inspection by Health Authorities**

This study will be monitored in accordance with the ICH GCP and any other applicable regulations. The site Monitor will perform visits to the study site at regular intervals.

The clinical study protocol, each step of the data capture procedure, and the handling of the data, including the final clinical study report, will be subject to independent Quality Assurance activities. Audits may be conducted at any time during or after the study to ensure the validity and integrity of the study data. Representatives of the Quality Assurance unit from the Sponsor or a designated organization, as well as Health Authorities, must be permitted to access all study documents and other materials at the site, including the Investigator Site File, the completed

---

CRFs, all IMP and IMP accountability records, and the original medical records or files for each subject.

## **10.5                   Changes to the Clinical Study Protocol**

Changes to the clinical study protocol will be documented in writing. Substantive amendments will usually require submission to the Health Authorities and to the relevant IEC/IRB for approval or favorable opinion. In such cases, the amendment will be implemented only after approval or favorable opinion has been obtained.

Minor (nonsubstantial) protocol amendments, including administrative changes, will be filed by the Sponsor and at the site. They will be submitted to the relevant IEC/IRB or to Health Authorities only where requested by pertinent regulations. Any amendment that could affect the subject's agreement to participate in the study requires additional informed consent prior to implementation following the process as described in Section 9.2.

## **10.6                   Clinical Study Report and Publication Policy**

### **10.6.1               Clinical Study Report**

After completion of the study, a clinical study report will be written by the Sponsor in consultation with the Coordinating Investigator following the guidance in ICH Topic E3.

### **10.6.2               Publication**

The first publication will include the results of the analysis of the primary endpoints and will include data from all study sites. The Investigator will inform the Sponsor in advance about any plans to publish or present data from the study. Any publications and presentations of the results (abstracts in journals or newspapers, oral presentations, etc.), either in whole or in part, by Investigators or their representatives will require review by the Sponsor before submission. The Sponsor will not suppress publication, but maintains the right to delay publication in order to protect intellectual property rights.

Posting of data on ClinicalTrials.gov is planned and will occur 12 months after the last study site visit of the final study subject or another appropriate date to meet applicable requirements.

**Appendices**

## Appendix I: Contraceptive Guidance and Woman of Childbearing Potential

### Definitions

#### Woman of Childbearing Potential (WOCBP)

A woman is considered fertile following menarche and until becoming post-menopausal unless permanently sterile. Permanent sterilization methods include hysterectomy, bilateral salpingectomy, and bilateral oophorectomy.

#### Women in the following categories are not considered WOCBP

##### 1. Premenopausal female with 1 of the following:

- Documented hysterectomy
- Documented bilateral salpingectomy
- Documented bilateral oophorectomy

Note: Documentation can come from the site personnel's: review of participant's medical records, medical examination, or medical history interview.

##### 2. Premenarchal

##### 3. Postmenopausal female

- Females who are postmenopausal (age-related amenorrhea  $\geq$  12 consecutive months and increased follicle-stimulating hormone [FSH]  $> 40$  mIU/mL), or who have undergone hysterectomy or bilateral oophorectomy are exempt from pregnancy testing. If necessary to confirm postmenopausal status, an FSH will be drawn at Screening.
- Females on HRT and whose menopausal status is in doubt will be required to use one of the nonhormonal highly effective contraception methods if they wish to continue their HRT during the study. Otherwise, they must discontinue HRT to allow confirmation of postmenopausal status before study enrollment.

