### 7.1.1 Screening and Baseline Procedures and Assessments

The screening procedures and baseline assessments will be completed up to 21 + 7 days before study treatment starts.

Subjects will be asked to sign the ICF at the start of the screening period and before any study-related investigations and assessments are started. The screening procedures and baseline assessments will be completed up to 21 + 7 days of signing the ICF and before receiving treatment. Failure to establish eligibility within 28 days would result in screening failure and the subject will be excluded from the study.

The subjects' information that will be documented during screening includes the demographic information (birth date as permitted by local regulations, sex, and race as permitted by local regulations) and the complete medical history, including the history of malignant disease, history of malignant disease drug therapy/radiotherapy/surgery, previous and ongoing medications, and baseline medical condition (concomitant medications and procedures and AEs will be monitored throughout the study treatment period). Moreover, an Emergency Medical Support card will be handed out at the baseline assessments visit.

During screening, subjects will undergo a complete physical examination, including recording body height and weight, vital signs, chest X-ray, 12-lead ECG, and a determination of the ECOG PS.

The screening laboratory examination includes hematology, coagulation, full serum chemistry, and full urinalysis (dipstick plus microscopic evaluation if indicated), will also be assessed at Screening for all subjects.

During screening, a serum  $\beta$ -human chorionic gonadotropin ( $\beta$ HCG) pregnancy test will be performed for females of childbearing potential, and blood hepatitis B virus and hepatitis C virus tests will be performed (may be analyzed locally) for all screened subjects as these conditions are study entry exclusion criteria (see Section 5.3.2). Females who are postmenopausal (age-related amenorrhea  $\geq$  12 consecutive months), or who have undergone hysterectomy or bilateral oophorectomy are exempt from pregnancy testing. If necessary to confirm postmenopausal status, FSH will be drawn at Screening.

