### **7.4.3 Clinical Laboratory Safety Assessments**

Blood and urine samples will be collected for the following clinical laboratory safety tests (Table 10), following the timing noted in the Schedule of Assessments (Table 1, Table 2, and Table 3). All samples should be clearly identified.

The Sponsor should receive a list of laboratory reference ranges before shipment of study drug. Any change in laboratory normal ranges during the study should be forwarded to Sponsor.

All clinical laboratory samples for the assessment of the relevant safety parameters, will be collected and analyzed locally. Local laboratory samples and results will be recorded in the eCRFs according to the eCRF completion guidelines. The report of the results must be retained as a part of the subject's medical record or source documents. Blood samples for the full safety tests will be taken from fasted subjects. If confirmation of a subject's postmenopausal status is necessary, an FSH level will also be performed at Screening.

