For female subjects of childbearing potential, a serum  $\beta$ HCG pregnancy test will be carried out during the Screening phase and a urine  $\beta$ HCG pregnancy test at the subsequent visits and at the Safety Follow-up visit of  $30 \pm 3$  days as indicated in the Schedules of Assessments ([Table 1](#), [Table 2](#), and [Table 3](#)). Results of the most recent pregnancy test (within the last 28 days) should be available prior to the next dosing of the study treatment. Subjects who are postmenopausal (age-related amenorrhea  $\geq 12$  consecutive months or FSH  $> 40$  mIU/mL), or who had undergone hysterectomy or bilateral oophorectomy are exempt from pregnancy testing.

Total volume of blood to be collected per subject will be approximately 20 mL for Screening and approximately 220 to 250 mL per cycle.

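### Sections 7.1.1 and 7.4.4 exempt from pregnancy testing some women whom Appendix I, read literally, still classes as of childbearing potential

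*Protocol*

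**What the plan says.** Inclusion criterion 10a (Section 5.3.1) takes the definition of a woman of childbearing potential (WOCBP) from Appendix I. Under its postmenopausal category, Appendix I requires two things together: age-related amenorrhea of at least "12 consecutive months and increased follicle-stimulating hormone [FSH", with FSH above 40 mIU/mL. It adds that FSH is drawn at Screening only where needed to confirm status.

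Three other places state who is exempt from testing:

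- **Section 7.4.4** joins the same two criteria the other way, "consecutive months or FSH" above 40 mIU/mL, and ends "or who had undergone hysterectomy or bilateral oophorectomy are exempt from pregnancy testing". The same paragraph opens "For female subjects of childbearing potential, a serum" test at Screening, and then asks for a urine "pregnancy test at the subsequent visits and at the Safety Follow-up visit of" 30 ± 3 days.
- **Section 7.1.1** uses amenorrhea alone, at least "12 consecutive months), or who have undergone hysterectomy or bilateral oophorectomy are exempt from pregnancy testing". It continues: "If necessary to confirm postmenopausal status, FSH will be drawn at Screening". Section 7.4.3 is conditional in the same way: where confirmation of "postmenopausal status is necessary, an FSH level will also be performed at Screening".
- **Table 1, footnote n** exempts postmenopausal women without saying who they are. It also requires a negative test on Day 1 of each cycle.

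**The concern.** Each of these sentences decides whether a given woman is tested, and they use different criteria. A site that enrolls a woman as WOCBP under Appendix I could then read Section 7.4.4, find that she meets its looser definition, and stop her on-treatment and follow-up tests.

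The stake is fetal exposure to a first-in-human drug. Section 3.4.2.1 says that no embryo-fetal toxicity study has been done and that effects on pregnancy cannot be excluded. Inclusion criterion 10b notes that the effect of M4112 on CYP3A4 is unknown and asks women on hormonal contraception metabolized by CYP3A4 to add double barrier contraception. Section 7.4.2 requires study treatment to stop immediately on pregnancy. Repeat testing is therefore the backstop if contraception fails, and later detection means longer exposure.

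**Working it through.** No formula applies. The check is to run each possible woman through each rule.

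**Inputs.** Appendix I: amenorrhea of at least 12 months and FSH above 40. Section 7.1.1: amenorrhea of at least 12 months. Section 7.4.4: amenorrhea of at least 12 months or FSH above 40. Footnote n has no criterion, so it cannot settle a disagreement. The woman considered has had no sterilizing surgery.

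**States.** Amenorrhea is met or not (2 states). FSH is measured above 40, measured at 40 or below, or not drawn (3 states). The third must be kept apart because the protocol makes the draw conditional. That gives 2 × 3 = 6 cases.

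| Amenorrhea ≥ 12 months | FSH (mIU/mL) | Appendix I | 7.1.1 | 7.4.4 | Result |
|---|---|---|---|---|---|
| Yes | > 40 | exempt | exempt | exempt | agree |
| Yes | measured ≤ 40 | WOCBP | exempt | exempt | **conflict** |
| Yes | not drawn | unclear | exempt | exempt | ambiguous |
| No | > 40 | WOCBP | tested | exempt | **conflict** |
| No | measured ≤ 40 | WOCBP | tested | tested | agree |
| No | not drawn | WOCBP | tested | tested | agree |

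**Reading the table.**

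1. With FSH above 40 and menses within 12 months, Appendix I and Section 7.1.1 agree that she is not exempt. Section 7.4.4 alone releases her, because either criterion is enough there.
2. With 12 months of amenorrhea and a measured FSH of 40 or below, she fails one of the two Appendix I criteria. Sections 7.1.1 and 7.4.4 both release her on amenorrhea.
3. With 12 months of amenorrhea and no FSH value, Appendix I points both ways. Its definition names FSH, but its next sentence draws FSH only if needed. This is unclear drafting, not a firm contradiction.

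**What the table does not show.** The cases are not equally likely, so the number of conflicting rows is not a measure of size. The documents do not say how many women fall in any row.

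**Surgery.** Hysterectomy and bilateral oophorectomy are treated alike throughout. Documented bilateral salpingectomy is listed only in Appendix I. That is not a conflict, because Section 7.4.4 asks for tests only in women of childbearing potential.

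**The case against.** The strongest reply is that childbearing potential is defined once, in Appendix I, and everything else should be read through it. Section 7.4.4 begins by requiring tests in women of childbearing potential, and footnote n wants a negative result on Day 1 of each cycle. A woman who is WOCBP under Appendix I is thus told to be tested by the very paragraph said to release her. To miss a test, a site would have to read the parenthesis alone, against the definition it used at enrollment. The FSH-only case is also nearly hypothetical: FSH is drawn to confirm menopause, so a menstruating woman has little protocol reason to have a value on record.

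Most of this stands as a limit on reach. A site that applies Appendix I throughout keeps testing these women, and the FSH-only case should be rare. It does not remove the contradiction. Section 7.4.4 supplies its own looser meaning of postmenopausal, and footnote n leaves the word undefined, so neither sends the site back to Appendix I. The amenorrhea case with low FSH is also less remote, since FSH is drawn exactly when status is in doubt.

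Two stronger readings are tempting. A reader might infer that tests before first dosing would be lost. The documents do not support that: inclusion criterion 11 requires negative tests at Screening and on Day 1 in every woman of childbearing potential. A reader might also infer that every amenorrheic woman without an FSH value is wrongly exempted. That fails too, because Appendix I itself makes the FSH draw conditional.

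**Conclusion.** The inconsistency is real and minor. Read literally, two groups who are WOCBP by the eligibility definition are exempt from testing: FSH above 40 with menses within 12 months (Section 7.4.4 only), and 12 months of amenorrhea with a measured FSH of 40 or below (Sections 7.1.1 and 7.4.4). A third group, amenorrhea with FSH not drawn, is ambiguous.

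The exposure lies in the on-treatment and follow-up tests, where a pregnancy could be found later than intended. Contraception under inclusion criterion 10b still applies. Dose escalation, DLT evaluation and every planned analysis are untouched.

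No number of women or lost tests can be derived. That the cases are rare is a judgment, resting on the conditional FSH draw and on a planned Part IA of about 24 subjects of both sexes. The conclusion assumes that a site may take the exemption sentences at face value. Section 7 of the final analysis plan reports that the study ended early with only Part IA completed, so the correction now matters mainly for any further amendment or reuse of this text.

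**What to change.** Two edits are needed, and the first is not enough alone.

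1. In Sections 7.1.1 and 7.4.4 and in Table 1 footnote n, remove the local definitions and exemption wording. Put one sentence in their place: *Pregnancy tests are not required in women who are not WOCBP as defined in Appendix I.* This also makes plain that documented bilateral salpingectomy is covered.
2. In Appendix I, keep both criteria and replace the conditional FSH sentence with: *FSH is measured at Screening in any woman claiming natural menopause who has no documented FSH above 40 mIU/mL; a woman without both criteria on record is tested as WOCBP.* Without this edit, amenorrhea with no FSH value stays ambiguous.

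The cost is amendment wording and a few extra FSH or urine pregnancy tests, both of which the schedule already provides for.
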